5.2 Informed Consent

The Informed Consent must be documented on the current IRB-approved version of the informed consent form. The consent process must also be documented in the site's Study Notebook. The Informed Consent must be obtained prior to performing any Study-specific procedures. The patient must be given a fully executed copy of the informed consent form. The site retains the original signed informed consent form.

5.3 Inclusion/Exclusion Criteria

All inclusion and exclusion criteria must be evaluated prior to subject enrollment and at the start of the ProLung Test protocol. Documentation that the subject meets all of the inclusion criteria and none of the exclusion criteria must be present in the subject's source documents in Site Study Notebook. If an exemption to the inclusion or exclusion criteria is granted by the Sponsor, such exemption will be recorded in the CRF.

5.4 Demographics and Relevant Health History

- a. The subject's gender, age, and ethnicity (patient's optional response) will be recorded.
- b. The subjects will be asked about their smoking history including pack-years smoking and how recently they discontinued smoking if applicable.
- c. The subjects will be asked about their past and current exposure to cancer-causing agents.
- d. The subjects will be asked about their current pulmonary symptoms.
- e. A brief medical and surgical history will be obtained. The medical history should include all significant current conditions, including recent illnesses and history, within two years of the time of the ProLung Test. The surgical history will include any major surgeries performed within five years of the date the ProLung Test is performed.

5.5 Physical Exam

A physical examination will be performed at the patient visit to assess the patient's general physical status. Physical characteristics of height, weight will be measured and recorded.

5.6 Concomitant Medication Assessment

The subject's usage of concomitant medications within the most recent 2 weeks will be recorded including name of the drug, dosage, and reason for use. Medications will include both prescription and over-the-counter drugs, but will EXCLUDE herbal or nutritional supplements.

5.7 ProLung Testing Session

The ProLung Test operator non-invasively measures certain anatomical locations on the surface of the skin. ProLung Test locations are displayed immediately prior to measurement and sequenced for the Operator performing the test. Real-time assessment of the quality of each measurement assists the operator to capture measurement data.

All operators involved in measuring subjects will have previously been trained and certified in use of the ProLung unit as provided by the Sponsor and described in detail in the Operator Training Manual. They will demonstrate competence based on criteria established by the Sponsor prior to using the ProLung Test on enrolled patients. The ProLung Test requires an average of 20 minutes. In previous clinical studies, time required to complete the ProLung Test ranged from 16 to 23 minutes.

Patient ProLung measurement data will be printed out at the end of each test session and placed into the subject's source document file. This print-out only contains summary information of the collected data and does not represent a complete data-file that is analyzed with the Algorithm. Weekly, ProLung Test data will also be stored to a Sponsor provided USB flash drive which is used to send ProLung Test data to the Sponsor through a secure Study file sharing website.

5.8 Additional Data Collection

Post-Measurement (following ProLung Test)

- Adverse Event assessment

- Tolerability Questionnaire: Following the ProLung Test, subjects will be asked to complete a brief questionnaire regarding their experience and perception of the procedure. The questions are:
 1. Did the test cause any discomfort? If so, please describe.
 2. Did the time required for measurement seem too long? If so, what amount of time seems reasonable?
 3. Would you agree to undergo measurement again? If not, what is the reason?
 4. Do you have any suggestions for improving the measurement procedure? If so, please describe.

5.9 End of Study

The subject's active participation in the Study is completed once the ProLung Test and the adverse event assessment have been completed. The subject's active participation concludes prior to the performance of the lung biopsy.

5.10 Follow-up Outcome Assessment

The outcomes of any ancillary diagnostic procedures conducted as part of normal clinical care will be collected for further analysis and the provided CRF page(s) will be completed as appropriate. The Study participant will sign a "Release of Medical Information" at the time of the consent process. All laboratory and radiological tests performed to further evaluate the abnormal chest CT will be obtained by the study team and kept as part of the participant's source document. This will include but are not limited to results of biopsies, sputum cytology, repeat chest CT scans, repeat chest radiography, MRI and PET scans.

Prior to the close of the Study, each site will obtain the most recent CT Report and History and Physical (if available) for all enrolled subjects who received a benign biopsy result or a CT follow-up showing stability to re-confirm that the subjects have remained free of malignancy.

5.11 Adverse Event Assessment

During, and immediately following the ProLung Test, subjects will be observed for any potential adverse event. Any unanticipated and unfavorable sign, e.g., a symptom described by the patient or noted by the site staff will be recorded as an adverse event in the source documents and CRF, and followed-up with more specific questions or actions as required.

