6.0 Adverse Events

6.1 Adverse Event

6.1.1 Adverse Event Definition

An adverse event is defined as any untoward medical occurrence in a patient or clinical investigation subject involved in the testing of a medical device and which does not necessarily have to have a causal relationship with the device.

An adverse event can therefore be any unanticipated and unfavorable sign, symptom or disease temporally associated with the use of a device, whether or not considered related to the product.

An AE includes:

- An exacerbation of a pre-existing illness or symptom
- Post-measurement (i.e. after the ProLung Test) events that occur as a result of protocol-mandated procedures
- A condition detected or diagnosed after device utilization

An AE does not include:

- The disease or disorder being studied or signs and symptoms associated with the disease/disorder unless there is an unexpected worsening of the subject's condition
- A pre-existing disease or condition present at the start of the Study that did not worsen
- Elective medical or surgical procedures unless resulting from a SAE

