6.1.2 Procedures for Adverse Event Reporting

Adverse events will be recorded from the time the subject has begun measurement with the device through Study completion. Any change in medical status or untoward event that occurs from the time the subject signs informed consent and undergoes ProLung measurement will be recorded as a baseline condition in the medical history.

Any unanticipated and unfavorable sign (e.g., a symptom or physical anomaly described by the subject or noted by the site staff) will be recorded as an adverse event. Changes in the subject's physical or mental condition or other responses must be reported as AEs if they are considered clinically significant by the Principal Investigator, if they fulfill SAE criteria or if they cause discontinuation from the Study.

AEs not resolved at the end of the ProLung Test will be followed after clinical Study completion or as long as medically relevant as judged by the Principal Investigator.

The Sponsor will conduct an evaluation of any unanticipated adverse device effect (UADE) in accordance with local regulations and report the results of the evaluation to the Investigator, IRB and any necessary authorities within 10 working days after the Sponsor first receives notice of such an event.

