### **C. Primary Safety Endpoint**

Since the device is not used in any patient treatment decisions in this study, there is no risk to the study subjects other than non-serious skin reactions to electrode patches used in testing. Therefore, this is a non-significant risk study. However, the frequency of occurrence of any adverse events will be reported to the extent these occur in the study.

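### The protocol's adverse event wording is inconsistent on whether expected reactions count, so mild electrode-site skin reactions may be recorded at one site and not at another

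*Protocol*

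**What the plan says.** The protocol describes what counts as an adverse event in three places, and the SAP adds a statement about expected risk.

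- **Protocol 6.1.1, definition.** The first sentence is broad: "An adverse event is defined as any untoward medical occurrence in a patient or clinical investigation subject involved in the testing of a medical device". The second sentence brings in a qualifier: "An adverse event can therefore be any unanticipated and unfavorable sign, symptom or disease temporally associated with the use of a device". The list of what an adverse event includes then names "Post-measurement (i.e. after the ProLung Test) events that occur as a result of protocol-mandated procedures", with no test of whether the event was expected.
- **Protocol 5.11, assessment at the test.** Observation is broad: "During, and immediately following the ProLung Test, subjects will be observed for any potential adverse event". The recording sentence that follows is qualified: "Any unanticipated and unfavorable sign, e.g., a symptom described by the patient or noted by the site staff will be recorded as an adverse event".
- **Protocol 6.1.2, reporting.** The section opens with an unqualified instruction to record adverse events from the start of measurement. It then repeats the qualified sentence: "Any unanticipated and unfavorable sign (e.g., a symptom or physical anomaly described by the subject or noted by the site staff) will be recorded". A further sentence says that changes in the subject's condition "must be reported as AEs if they are considered clinically significant by the Principal Investigator, if they fulfill SAE criteria or if they cause discontinuation".
- **SAP V.C, safety endpoint.** It states that "there is no risk to the study subjects other than non-serious skin reactions to electrode patches used in testing", and that the frequency of any adverse events will be reported. SAP XI tabulates them descriptively with 95% limits.

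Protocol 3.3 draws the safety data from everyone enrolled in either phase.

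**The concern.** Whether an event was anticipated normally decides if it needs evaluation as an unanticipated adverse device effect. It does not normally decide whether the event is an adverse event at all. Here the word appears in both sentences that tell site staff what sign to write down. The one effect that the SAP expects from the device is, by being named, anticipated.

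Safety and tolerability is Specific Aim 3 of the protocol, and SAP III puts safety into the primary hypothesis. The safety result is a simple frequency of adverse events. If the expected reaction can be left out before it reaches the CRF, a low percentage partly reflects the recording rule. If sites resolve the wording differently, the pooled percentage mixes two definitions.

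**Working it through.** The plan states no adverse event rate, so there is no figure to reproduce. The check is to take one test case through each rule. The case is mild redness under an electrode, noticed just after the test. It is expected, not judged clinically significant, not serious, and does not lead to discontinuation.

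| Rule | Condition on being unanticipated? | Does it call for the redness to be recorded? |
|---|---|---|
| 6.1.1, first sentence | No | It is an adverse event |
| 6.1.1, second sentence | Yes | Not covered, though the sentence says what an event *can* be |
| 6.1.1, inclusion list | No | It is an adverse event: the study procedure caused it, after measurement |
| 6.1.2, opening sentence | No | Yes, if the broad definition is used |
| 6.1.2, sentence on signs | Yes | No |
| 6.1.2, sentence on changes in condition | No, but it has three other triggers | No: none of the three is met |
| 5.11, observation sentence | No | Observed; the sentence does not deal with recording |
| 5.11, recording sentence | Yes | No |

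1. The definition's first sentence and inclusion list make the redness an adverse event.
2. Neither of the two sentences on recording signs requires an entry for it, and the additional triggers in 6.1.2 do not reach it.
3. The protocol does not say which wording prevails. Two sites can each follow a stated rule and treat the same redness differently.
4. The tolerability questionnaire (5.8) does not close the gap. Its first question asks about discomfort of any kind, not skin findings, and nothing sends the answers to the adverse event record or to the SAP XI table.

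**Can the shortfall be sized?** Only with assumed rates. Suppose that 1%, 5% or 10% of the 174 paired validation subjects had a mild reaction. That is 174 × 0.01 = 1.7, 174 × 0.05 = 8.7 or 174 × 0.10 = 17.4 subjects. If none were recorded and no other event occurred, the exact two-sided 95% upper limit would be 1 − 0.025^(1/174) = 2.1%.

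However, 174 is the paired-result set and not the safety population of Protocol 3.3. Adding the 200 algorithm-development patients in SAP V.A.1 gives at least 200 + 174 = 374, and the limit for 0/374 is 1 − 0.025^(1/374) = 1.0%. The rates are assumptions, and zero recording needs every site to take the narrow reading. These figures show only that the answer depends on inputs the documents do not give.

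**The case against.** A reader might infer that sites record only unanticipated signs, so that the safety table is bound to miss the one effect it expects. The documents do not support that, for four reasons.

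- No sentence says *only*. Sections 5.11 and 6.1.2 say that unanticipated signs will be recorded; they do not say that other signs will not be. The opening of 6.1.2 is unqualified, and the inclusion list in 6.1.1 fits an electrode reaction.
- The sentence in 6.1.2 on clinical significance, SAE criteria and discontinuation reads most naturally as an added set of mandatory triggers. It is not worded as a filter on everything else.
- The idea that skin reactions are anticipated comes from the SAP. The supplied protocol text names no such reaction, and its safety information (Appendix I, 3.5) expects no health risk or discomfort from the current. A site working from that text could treat redness as unanticipated and record it even under the narrow wording. The consent pages are not available, so what else sites were told cannot be checked.
- SAP V.A.1 already gives 111 malignant and 63 benign validation patients. Its risk statement therefore postdates those diagnoses and is weak evidence of what sites anticipated when they recorded events.

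All four points stand against the claim of certain loss. They do not remove the inconsistency. Whether a mild reaction is recorded still depends on which sentence a site follows and on what it happens to anticipate. The safety analysis is descriptive and the event is mild, which limits the consequence but does not make the wording consistent.

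**Conclusion.** The inconsistency is real and should be corrected. Under the narrow wording a mild, expected electrode-site reaction *need not* be recorded; under the broad wording it is an adverse event. Recording can differ between sites, and the SAP XI rate may be understated.

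The size cannot be estimated from the documents. It runs from nothing, if every site used the broad definition or regarded skin reactions as unanticipated, to all mild expected reactions, if every site used the narrow wording. Any understatement requires that some sites regarded these reactions as anticipated, took the recording sentence as limiting, and did not judge the reaction clinically significant. The documents show that this course is open to a site, not that any site took it.

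PPV, NPV and the other effectiveness analyses are not affected.

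**What to change.** 1. **Protocol wording.** Reconcile 5.11, 6.1.1 and 6.1.2 by removing *unanticipated* as a condition for recording an adverse event. This must include the second sentence of 6.1.1, or the inconsistency remains. Keep the word for the evaluation of unanticipated adverse device effects.
2. **SAP XI table.** Show electrode-site skin reactions on a separate line, with everyone enrolled in either phase as the population, in line with Protocol 3.3.
3. **Data already collected.** A wording change cannot recover past entries. Tabulate questionnaire answers that describe a skin reaction separately, labelled by source. Do not merge them with general discomfort, which is a different complaint. State as a limitation the recording rule under which the data were collected.

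The cost is an amendment handled under Protocol 9.6, a site memo, one table line and a read-through of the questionnaire free text. No visit or procedure is added. The downside is a slightly higher count of non-serious adverse events.

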6.0 Adverse Events

6.1 Adverse Event

6.1.1 Adverse Event Definition

An adverse event is defined as any untoward medical occurrence in a patient or clinical investigation subject involved in the testing of a medical device and which does not necessarily have to have a causal relationship with the device.

An adverse event can therefore be any unanticipated and unfavorable sign, symptom or disease temporally associated with the use of a device, whether or not considered related to the product.

An AE includes:

- An exacerbation of a pre-existing illness or symptom
- Post-measurement (i.e. after the ProLung Test) events that occur as a result of protocol-mandated procedures
- A condition detected or diagnosed after device utilization

An AE does not include:

- The disease or disorder being studied or signs and symptoms associated with the disease/disorder unless there is an unexpected worsening of the subject's condition
- A pre-existing disease or condition present at the start of the Study that did not worsen
- Elective medical or surgical procedures unless resulting from a SAE

6.1.2 Procedures for Adverse Event Reporting

Adverse events will be recorded from the time the subject has begun measurement with the device through Study completion. Any change in medical status or untoward event that occurs from the time the subject signs informed consent and undergoes ProLung measurement will be recorded as a baseline condition in the medical history.

Any unanticipated and unfavorable sign (e.g., a symptom or physical anomaly described by the subject or noted by the site staff) will be recorded as an adverse event. Changes in the subject's physical or mental condition or other responses must be reported as AEs if they are considered clinically significant by the Principal Investigator, if they fulfill SAE criteria or if they cause discontinuation from the Study.

AEs not resolved at the end of the ProLung Test will be followed after clinical Study completion or as long as medically relevant as judged by the Principal Investigator.

The Sponsor will conduct an evaluation of any unanticipated adverse device effect (UADE) in accordance with local regulations and report the results of the evaluation to the Investigator, IRB and any necessary authorities within 10 working days after the Sponsor first receives notice of such an event.

6.2 Serious Adverse Event

6.2.1 Serious Adverse Event Definition

An adverse event is considered serious if it:

- Occurs during Study measurement (ProLung Test) or immediately thereafter and,
- Meets any of the criteria outlined in the following section

An SAE is any adverse event that results in any of the following outcomes:

- Death or is life-threatening: A life-threatening SAE is any SAE that places the subject in the opinion of the Principal Investigator, at immediate risk of death from the reaction as it occurred. It does not include a reaction that, had it occurred in a more serious form, might have caused death
- Persistent or significant disability/incapacity
- Inpatient hospitalization or prolongation of existing hospitalization

Important medical events that may not result in death, be life-threatening, or require hospitalization may be considered a serious adverse event when, based upon appropriate medical judgment, they may jeopardize the subject, and may require medical or surgical intervention to prevent one of the outcomes listed in this definition. Scheduled and/or elective hospitalizations will not be defined as serious adverse events for this clinical Study.

6.2.2 Procedures for Serious Adverse Event Reporting

The Principal Investigator must inform the Sponsor and the Medical Monitor within 24 hours of becoming aware of any SAE that occurs during the course of the clinical Study. The Principal Investigator may communicate the event to the Sponsor or Medical Monitor; however, a completed SAE form must be faxed or scanned and emailed to the Medical Monitor and to the Sponsor within 24 hours of the initial reporting. All serious events must be reported, whether or not they are considered causally related to the device utilization. Appropriate clinical, diagnostic, and laboratory measures must be performed to delineate the cause of the SAE in question and the results reported. All tests that reveal an abnormality that is considered device related should be repeated at appropriate intervals until:

- The cause is determined
- A return to baseline value occurs
- Stable results are obtained over 2 to 3 consecutive readings that are clinically acceptable and safe for the subject

The Principal Investigator is required to assess the causal relationship to the Study device for each SAE to determine if the event is associated with the use of the device. Events should be classified as associated with the use of the device if there is a reasonable probability that the experience may have been caused by the device.

The Sponsor will conduct an evaluation of any UADEs in accordance with 21 CFR 812.46(b) and report the results of the evaluation to the Investigator, IRB and FDA within 10 working days after the Sponsor first receives notice of the effect in accordance with 21 CFR 812.150(b(1)). The Sponsor will terminate the investigation when a determination has been made that an unanticipated adverse device effect presents

an unreasonable risk to subjects. Termination will occur no later than 5 working days after the Sponsor makes the determination and not later than 15 working days after the sponsor first received notice of the effect in accordance with 21 CFR 812.46(b)(2).

7.0 Data Management

7.1 Data Collection

The site study team will make data entry on the case report forms (CRF)s and keep records of the subject's visit in the source documents for that site. The Principal Investigator or designee will be responsible for the timely recording of patient data.

To ensure that correct data have been entered on the CRF, CRFs will be 100% source-data verified by a Monitor from the Sponsor, who will notify the Principal Investigator or designee regarding questions or missing data. When data have been entered in the CRF, signed by the Principal Investigator, and all questions and/or corrections have been resolved and verified, the original of each CRF page(s) will be collected by the Sponsor. The PI will retain a copy of completed and monitored CRF pages. Any remaining questions or missing data subsequent to retrieval of a CRF page from a site will be noted on Data Clarification Forms (DCFs), which will be sent to the Principal Investigator. DCFs should be completed by the Study site and signed by the Principal Investigator in a timely manner.

ProLung Test subject data will be sent to the Sponsor on a weekly basis as subjects are enrolled.

